6.5.3.2. Diarrhea Management

Due to irinotecan-induced diarrhea, consider using cefixime (8 mg/kg/day) or an available equivalent of oral cephalosporin (i.e., cefpodoxime 10 mg/kg/day divided BID; maximum dose 400 mg/day) starting 2 days prior to first irinotecan dose and continued until 3 days after the last irinotecan dose per cycle. For patients receiving 5 days of irinotecan, the total course of diarrhea prevention is 10 days.

6.5.3.3. Allergic Reaction due to Dinutuximab

Prophylactic Antihistamine

- Consider administration of an antihistamine, such as diphenhydramine (0.5 to 1 mg/kg; maximum dose 50 mg) 20 minutes prior to dinutuximab and every 4 to 6 hours as tolerated during the dinutuximab infusion.

Mild Allergic Reactions: limited to Grade 1-2 rash, flushing, urticaria, and/or dyspnea

Suggested management of mild allergic reactions includes

- Decrease dinutuximab infusion rate to 50%
- Administer an H1 blocker, such as diphenhydramine or cetirizine
- Administer H2 blocker
- When symptoms resolve, resume original infusion rate

- If symptoms recur, again decrease infusion rate to 50%
- Infusion MUST be stopped after 20 hours even if full dose has not been administered; document total amount of dinutuximab infused.

Moderate to Severe Allergic Reactions: includes any of the following: symptomatic bronchospasm, allergy-related angioedema, generalized edema, hypotension, or anaphylaxis (Grade 3 or 4)

Suggested management of moderate to severe allergic reactions includes

- Immediately stop dinutuximab infusion
- Evaluate airway, breathing, and circulation
- Follow institutional guidelines for rapid response or critical care response team
- For airway concerns:
 - Administer oxygen and albuterol for bronchospasm
 - Administer IV diphenhydramine
 - Administer epinephrine (1:1000 IM recommended) for upper airway involvement or if accompanied by circulatory collapse
 - Administer IV hydrocortisone (1-2 mg/kg) for anaphylaxis with cardiovascular collapse, if ≥ 2 doses epinephrine are required, or for moderate to severe symptoms that recur upon dinutuximab rechallenge.
- For hypotension in the setting of allergic reaction
 - Give 20 mL/kg normal saline bolus
 - Stop or adjust narcotics and sedating H1 blockers
 - Consider use of Trendelenburg position
 - See previous section for hypotension management.
- For mild bronchospasm or angioedema without impact on breathing and that completely resolves without epinephrine or hydrocortisone, dinutuximab infusion may resume at 50% rate
- For hypotension that resolves following fluid bolus, dinutuximab infusion may resume at 50% rate on the same day of the reaction
- If symptomatic angioedema or bronchospasm recurs after dinutuximab infusion resumes, then discontinue infusion for that day
- If symptoms resolved completely on the day dinutuximab was discontinued, then resume the following day with hydrocortisone 1-2 mg/kg IV premedication. This rechallenge should be in the intensive care unit
- If bronchospasm or angioedema requires epinephrine, permanently discontinue dinutuximab
- For bronchospasm or angioedema with hypotension requiring volume resuscitation, refer to hypotension guidance in Section 6.5.3.1.

6.5.3.4. Capillary Leak Syndrome (\geq Grade 3)

Management of capillary leak syndrome:

- Stop dinutuximab infusion

- Administer oxygen and fluids as appropriate
- Diuretics should be used with caution and hypotension should be avoided
- If symptoms persist on the same day or recur on subsequent days within the same cycle, discontinue dinutuximab for that cycle
- Only resume when capillary leak symptoms are \leq Grade 2
- If resolves, resume dinutuximab at 50% rate the same day and for remaining doses within the same cycle. For subsequent cycles, the dinutuximab may be given at the full rate
- If therapy-related capillary leak syndrome requires pressors for \geq 24 hours or any duration of mechanical ventilation, the patient must discontinue all study drugs.

6.5.3.5. Renal Insufficiency

- For borderline hypotension, consider the possibility of renal hypoperfusion and administer volume as appropriate
- If creatinine is $\geq 2 \times$ ULN and elevation persists despite optimized fluid management, hold dinutuximab infusion
- Modify concomitant medications that may contribute to or be affected by renal insufficiency
- If urine output normalizes and creatinine returns to $< 2 \times$ ULN, the dinutuximab infusion may resume at 50% rate. If renal function returns to normal by the next day, dinutuximab infusion may resume at the full rate
- If urine output has not normalized and/or creatinine remains $\geq 2 \times$ ULN by Day 7, no further dinutuximab should be given in the cycle. If renal function has normalized by planned start date of next cycle, then retreatment is permitted.

6.5.3.6. Hyponatremia (\geq Grade 3; Na < 130 mEq/L)

- Switch hypotonic fluids to isotonic fluids as compatibilities allow
- Do not administer oral free water
- Correct fluid losses caused by diarrhea
- Use 3% saline only if:
 - Hyponatremia leads to seizure
 - Sodium level decreases by > 10 points in ≤ 6 hours
 - Sodium level < 117 mEq/L
- If Grade 4 hyponatremia persists despite optimal fluid management, do not administer dinutuximab during the rest of the cycle. Monitor sodium levels closely in the subsequent cycle
- If Grade 4 hyponatremia recurs in the subsequent cycle despite optimal fluid management, permanently discontinue all study drugs.

6.5.3.7. Fever in the Absence of Hypotension

- Administer antipyretics
- If fever is persistent, adjust fluids to account for insensible losses
- Obtain blood culture and then administer empiric antibiotics per institutional policy.

6.5.3.8. Treatment-Related Pain

- For patients who experience pain that is uncontrolled by narcotics, no further dinutuximab should be given during a given cycle
- For recurrent uncontrolled pain in a subsequent cycle, discontinue all study drugs
- For patients requiring intravenous narcotics for ≥ 48 hours after completion of dinutuximab infusion, gabapentin or similar agent should be initiated (if not already being administered)
- If pain requiring intravenous narcotics for ≥ 48 hours after completion of dinutuximab infusion recurs in a subsequent cycle, discontinue all study drugs.

Pain Management

- Non-opioid analgesics (i.e., acetaminophen and ibuprofen): before each dinutuximab infusion and every 4-6 hours as needed for pain and/or fever
- Gabapentin:
 - 10 mg/kg/day 3 days before dinutuximab infusion
 - 2 \times 10 mg/kg/day 2 days before dinutuximab infusion
 - 3 \times 10 mg/kg/day 1 day before dinutuximab infusion; can be paused between cycles or continuous during cycles
 - Taper dose at discontinuation of dinutuximab
- Morphine:
 - 0.02-0.05 mg/kg/hour continuous infusion prior to dinutuximab infusion and
 - 0.02-0.05 mg/kg/hour or as required for adequate pain control during dinutuximab infusion and for 2 hours after infusion is complete
 - Discontinue or reduce infusion rate (e.g., 0.01 mg/kg/hour) 2 hours after infusion each day, as tolerated
- If morphine is contraindicated, consider fentanyl or hydromorphone per investigator discretion
- Lidocaine and/or ketamine can be considered for pain that is not manageable using the above medications
- Refer to Section 6.1.1 for infusion rate adjustments of dinutuximab.

6.5.3.9. Visual Changes

- Discontinue current course of dinutuximab for patients who develop dilated pupils with sluggish light reflexes
- If papillary abnormalities remain stable or improve before the next course, resume dinutuximab at 50% of prior dose
- If there is no worsening of ocular toxicity at the reduced dose, then full dose may be given in subsequent courses
- If ocular toxicity worsens or recurs after resuming the full dose, permanently discontinue all study drugs
- Isolated changes in accommodation do not require dose reductions.

6.5.3.10. Serum Sickness

- Identification of serum sickness is important. Signs and symptoms include arthralgias/arthritis, splenomegaly, lymphadenopathy, glomerulonephritis in the presence of persistent fevers, and cutaneous eruptions
- Serum sickness typically develops 1 to 3 weeks after administration of the causative agent but can develop within 12-36 hours in sensitized patients
- Patients with Grade 2 serum sickness should receive antihistamines
- Patients with \geq Grade 3 serum sickness should permanently discontinue all study drugs.

6.5.3.11. Neurotoxicity

- For Grade 3 sensory or motor neuropathy, discontinue dinutuximab for the remainder of the current cycle
- If neuropathy resolves by start of next cycle, reduce dinutuximab dose to 50%
- If neuropathy symptoms do not resolve, or if they recur, then permanently discontinue all study drugs
- Grade 4 neurotoxicity requires permanent dinutuximab discontinuation.

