6.5.3. Supportive Management of Anticipated Dinutuximab-Associated Toxicities (Part C Only)

Side effects during dinutuximab infusion should be anticipated and will frequently occur even with use of pretreatment medications. The need to slow, pause, or discontinue infusion should be anticipated and is not unexpected. Refer to Section [6.6.1.3](#) for dose modifications of dinutuximab.

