	Recurrent despite reductions	Hold until \leq Grade 1, then reduce dose	No change	No change	Reduce to 8.75 mg/m ² /dose	
Grade 4 ($>20x$ ULN AST or ALT) Any Duration ^b	1 st Event	Discontinue all study drugs				
ALT Increase (Any Grade) Causing Cycle Delay >14 days ^{b,c}	1 st Event	Modify per Section 6.6.1.1	No change	No change	Reduce to 13.13 mg/m ² /dose	
	Recurs despite dinutuximab dose reduction	Discontinue all study drugs				

Abbreviations: ALT = alanine aminotransferase; AST = aspartate aminotransferase; ULN = upper limit of normal.

^a Determination of persistent events will be at the discretion of the investigator. Recurrent toxicity refers to the same event occurring within the next 8 weeks (as measured from the stop date of the preceding event).

^b Grade ≥ 3 ALT increased is a trigger for additional assessments and possibly hepatic monitoring. See Section 8.2.1.1 for additional guidance for hepatic monitoring.

^c Delay of >14 days indicates more than 35 days from Day 1 of previous cycle.

Part C Dose Modifications for Miscellaneous Toxicity					
		Abemaciclib	Irinotecan	Temozolomide	Dinutuximab
ILD or Pneumonitis	Persistent or recurrent ^a Grade 2 despite maximal supportive care ^b	Hold until \leq Grade 1 then reduce dose	Hold until \leq Grade 1 then reduce dose	No change	No change
	Grade 3 or 4	Discontinue all study drugs			
Nonhematologic Toxicity not Otherwise Described Above	Grade 2 Persistent or recurrent ^{a, b}	Hold until \leq Grade 1 then reduce dose	No change	No change	No change
	Grade 3 or 4	Hold until \leq Grade 1 then reduce dose	Hold until \leq Grade 1 then reduce dose	Hold until \leq Grade 1 then reduce dose	No change
Any AE-Associated Cycle Delay of >21 Days^c	1 st Event	Discontinue all study drugs			

Abbreviations: AE = adverse event; ILD = interstitial lung disease.

- ^a Determination of persistent events will be at the discretion of the investigator. Recurrent toxicity refers to the same event occurring within the next 8 weeks (as measured from the stop date of the preceding event).
- ^b Does not resolve with maximal supportive measures within 7 days to baseline or Grade 1 unless deemed clinically insignificant by the investigator.
- ^c Delay of >21 days indicates more than 42 days from Day 1 of previous cycle. Exceptional circumstances may be allowed upon approval by CRP/CRS.

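### Protocol Sections 6.5.3 and 6.6.1.3 conflict on some severe dinutuximab toxicities in Part C, and neither says which governs

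*Protocol*

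**What the plan says.** Section 6.5.3 covers the toxicities expected from dinutuximab. Its opening paragraph refers the reader to Section 6.6.1.3 "for dose modifications of dinutuximab", but its subsections then give dosing instructions of their own:

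- **Grade 3 neuropathy (6.5.3.11):** "For Grade 3 sensory or motor neuropathy, discontinue dinutuximab for the remainder of the current cycle". Next, "If neuropathy resolves by start of next cycle, reduce dinutuximab dose to 50" per cent. Finally, "If neuropathy symptoms do not resolve, or if they recur, then permanently discontinue all study drugs".
- **Grade 4 (6.5.3.11):** "Grade 4 neurotoxicity requires permanent dinutuximab discontinuation". The Part C paragraph of Section 6.6 adds that a patient who must stop any one study drug stops all protocol therapy.
- **Serum sickness (6.5.3.10), from Grade 3 upwards:** "Grade 3 serum sickness should permanently discontinue all study drugs".
- **Capillary leak of Grade 3 or higher (6.5.3.4):** dinutuximab is stopped for the cycle if symptoms persist that day or recur within the cycle.
- **Grade 4 hyponatremia that persists (6.5.3.6):** no more dinutuximab in that cycle.

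The Part C tables in Section 6.6.1.3 have rows for hematological toxicity, diarrhea, vomiting and dehydration, hepatotoxicity, and lung disease. The miscellaneous table then has a row titled "Nonhematologic Toxicity not Otherwise Described Above". At Grade 3 or 4 that row holds abemaciclib, irinotecan and temozolomide until Grade 1 or lower and then reduces them. Its entry for dinutuximab is no change.

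**The concern.** None of the five events listed from Section 6.5.3 has its own row in the tables. A site that follows the pointer to Section 6.6.1.3 arrives at the catch-all row, which leaves alone the drug that Section 6.5.3 stops and acts on three drugs that Section 6.5.3.11 does not mention for a first Grade 3 neuropathy. Two sites could treat the same event differently and both be following the protocol.

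The first stake is patient safety, because exposure to dinutuximab after a severe reaction to it depends on the section read. The second is the Stage 1 decision. Rule B (Protocol Sections 4.1.2 and 9.5; SAP Sections 6.1.2 and 7.7.2) counts patients who discontinue for a treatment-related adverse event before a set number of cycles. If one section ends treatment and the other does not, that count depends on which was followed. The dose-intensity summaries for each drug (SAP Section 7.2.1) would mix the two practices.

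**Working it through.** The plan states no figure to reproduce. The check sets the instructions side by side and looks for a rule of precedence.

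| Event | Section 6.5.3 | Section 6.6.1.3 catch-all row, Grade 3 or 4 |
|---|---|---|
| Grade 3 neuropathy, first event | Dinutuximab off for the cycle, then half dose if resolved; silent on the other drugs | Dinutuximab unchanged; other three held, then reduced |
| Grade 3 neuropathy, unresolved or recurrent | All drugs stopped | As above |
| Grade 4 neurotoxicity | Dinutuximab stopped permanently; through Section 6.6, all therapy | As above |
| Serum sickness, Grade 3 or higher | All drugs stopped | As above |
| Capillary leak, Grade 3 or higher, persistent or recurrent | Dinutuximab off for the cycle | As above |
| Grade 4 hyponatremia, persistent | Dinutuximab off for the cycle | As above |

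The other three drugs are abemaciclib, irinotecan and temozolomide. The tables have no GM-CSF column.

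**Size for one patient.** The planned dose is 17.5 mg/m²/day for 4 days, so 4 × 17.5 = 70 mg/m² per cycle.

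- Grade 3 neuropathy after the second infusion: Section 6.5.3.11 gives 2 × 17.5 = 35 mg/m² in that cycle; the catch-all row gives 70.
- Next cycle, if resolved: 0.5 × 17.5 = 8.75 mg/m²/day, so 4 × 8.75 = 35 mg/m², against 70.

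**Is the no-change entry only a blank?** No. The same tables reduce dinutuximab elsewhere: by 25% for some neutropenia, and to 13.13 or 8.75 mg/m² per dose for some diarrhea and liver events. The entry is an instruction.

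**Is there a precedence rule?** None was found.

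- Sections 6.5.3, 6.6, 6.6.1, 6.6.1.1 and 6.6.1.2 all send the reader to 6.6.1.3 for Part C.
- Section 6.6.1.3 does not refer back to 6.5.3. Its fallbacks for unlisted toxicities cover abemaciclib and irinotecan only.
- The rule in Section 6.6.1 that lets the investigator adjust only the causal drug is limited to Parts A and B.

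**Which events move Rule B?**

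- A first Grade 3 neuropathy that resolves: neither section requires permanent discontinuation, so the count does not change.
- Serum sickness of Grade 3 or higher, and Grade 4 neurotoxicity: Section 6.5.3 (with 6.6 for the latter) ends treatment; the catch-all row does not.
- Recurrent neuropathy: Section 6.5.3.11 ends treatment; the catch-all row holds and reduces.
- Unresolved neuropathy: the sections differ in the same way, but can converge, because Section 6.6.1.3 also ends treatment once an adverse event delays a cycle by more than 21 days.

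**The case against.** The best defence is that the word *above* in the catch-all row's title reaches back to Section 6.5.3, which comes earlier and describes these events specifically. The row would then exclude them, and the specific text would override the general. That reading is possible, so this is a conflict on the natural reading and not an unavoidable one. But the row closes a run of tables and most naturally refers to them. Section 6.5.3 is presented as supportive management and itself defers to 6.6.1.3 for dinutuximab dosing. Nothing states the wider reading.

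A reader might also infer more than the documents support:

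- **That the table route creates extra DLTs**, because holding drugs in Cycle 1 can bring a patient below 75% of planned doses. Section 4.1.3 already makes Grade 3 or higher neuropathy or serum sickness in Cycle 1 a DLT if it is clinically significant and related, and neither is among the listed exceptions. Section 6.6.1 then suspends treatment and reduces abemaciclib. The 75% rule also covers dinutuximab: missing two of its four doses leaves 50%. For these events the rule does not separate the readings. Electrolyte events have their own exception, and no DLT claim is made about them.
- **That abemaciclib continues under Section 6.5.3.** For a first Grade 3 neuropathy that section is silent on abemaciclib, and for serum sickness it stops it. For the same reason, a count of differing drug columns depends on how silence is read.
- **That every toxicity in Section 6.5.3 conflicts with the tables.** Uncontrolled pain ("no further dinutuximab should be given during a given cycle") and visual changes are triggered by clinical description, not by CTCAE grade. Grade 3 hyponatremia brings no dinutuximab change. Capillary leak that resolves, and some allergic reactions, lead to a pause or slower rate and not a lower dose.

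**Conclusion.** The point holds in limited form. It is clearest for Grade 3 neuropathy, Grade 4 neurotoxicity and serum sickness of Grade 3 or higher. It extends to persistent or recurrent capillary leak of Grade 3 or higher and to persistent Grade 4 hyponatremia.

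For one patient the difference is large: half or all of the planned dinutuximab in the cycle after a resolved Grade 3 neuropathy, and stopping or continuing treatment after serum sickness or Grade 4 neurotoxicity. For the trial it cannot be sized. The documents give no rate for these events, and the Rule B thresholds are not shown in the public text. Each patient classified differently, within the cycles that Rule B covers, moves its count by one. A reader might infer a bias in the response rate, but nothing in the documents allows one to be estimated or given a direction.

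The conclusion assumes that the catch-all row refers to the Section 6.6.1.3 tables and that no other document available to sites settles precedence. No view is taken on which clinical action is right.

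**What to change.** Reconcile Sections 6.5.3 and 6.6.1.3 in one of two ways. Either give each of these events its own row in the Part C tables, with the action for every study drug agreed by the sponsor's clinicians. Or state in the catch-all row whether events covered by Section 6.5.3 are excluded and which section governs. In either case, add a reference from 6.6.1.3 back to 6.5.3 and bring the pointer at the start of 6.5.3 into line.

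The cost is protocol wording and site training. No patients, visits or analyses are added. If Part C patients have already had such events, the sponsor should record which section was followed, so that the Rule B count and the dose-intensity summaries can be interpreted.

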6.6. Dose Modification

In the event of a cycle delay due to logistical reasons (e.g. due to patient availability), the patient should continue on abemaciclib if the patient has adequate drug supply. If a patient's treatment is interrupted as a result of not having sufficient drug supply, the cycle may be delayed up to 7 days (and not be considered a protocol violation). In exceptional circumstances, a delay >7 days is permitted upon agreement between the investigator and the Lilly CRP/CRS. In exceptional cases, for planned delays (including but not limited to vacation or holidays), additional study treatment may be dispensed upon consultation with Lilly CRP/CRS.

For patients undergoing surgery, refer to the following guidelines for abemaciclib dose modifications:

- For minor surgeries and procedures (e.g. ambulatory), investigators should treat as clinically indicated and closely monitor any signs of infection or healing complications.
- For major surgeries, the recommendation is to suspend dosing of abemaciclib for at least 7 days before and may be resumed as clinically indicated.
- Consider monitoring neutrophils and platelets before surgery and before resuming abemaciclib. The scars should be aseptic and the healing process should be reasonable before resuming abemaciclib.
- Dose suspensions ≥ 21 days must be discussed with Lilly CRP/CRS.

Parts A and B:

Patients may discontinue chemotherapy while continuing abemaciclib monotherapy (i.e. due to minor chemotherapy-associated toxicities) upon discussion with the Lilly CRP/CRS. In the event that abemaciclib must be discontinued, patients may continue to receive chemotherapy. For each study drug, if further dose reductions are required beyond the allowable dose reductions outlined below, the drug should be discontinued.

Part C:

For each study drug, if further dose reductions are required beyond the allowable dose reductions outlined below, the drug should be discontinued. If any study drug must be discontinued, the patient must discontinue all protocol therapy. Discontinuation of chemotherapy after Cycle 12 is permitted at the investigator's discretion without having to discontinue abemaciclib, dinutuximab, and GM-CSF (refer to Section 4.1). For dose modification guidance specific to Part C, see Section 6.6.1.3. For dose modifications of GM-CSF, refer to Section 6.6.1.4.

Parts A and B: Starting Dose and Adjustments for Abemaciclib-Related Toxicities^a

Dose at Enrollment	First Reduction	Second Reduction
150 mg	100 mg	50 mg
125 mg	75 mg	50 mg
100 mg	75 mg	50 mg
75 mg	50 mg	25 mg
50 mg	25 mg	Not permitted; must discontinue
25 mg	Not permitted; must discontinue	

^a Reduced doses of abemaciclib should still be taken twice daily.

Part C: Starting Dose and Adjustments for Abemaciclib-Related Toxicities^a

Dose at Enrollment	First Reduction	Second Reduction
100 mg	75 mg	50 mg
75 mg	50 mg	25 mg
50 mg	25 mg	17.5 mg
25 mg	17.5 mg	10 mg
22.5 mg	15 mg	10 mg
20 mg	15 mg	10 mg
17.5 mg	12.5 mg	Not permitted; must discontinue
15 mg	10 mg	
12.5 mg	Not permitted; must discontinue	
10 mg		

^a Reduced doses of abemaciclib should still be taken twice daily.

Dose Levels and Adjustments for Irinotecan-related Toxicities

Dose at Enrollment	First Reduction	Second Reduction
50 mg/m ²	-25%	-50%

Dose Levels and Adjustments for Temozolomide-related Toxicities

Dose at Enrollment	First Reduction	Second Reduction
150 mg/m ²	100 mg/m ²	75 mg/m ²
100 mg/m ²	75 mg/m ²	

6.6.1. Dose Modification Guidance due to Toxicity

- Treatment will be suspended for DLT and may be resumed after resolution. The abemaciclib dose must be reduced. If no further dose reductions are available (refer to Section 6.6), the patient must discontinue abemaciclib. For toxicities that are not dose-limiting, see Section 6.6.1.1.
- Investigators will document whether or not an AE has a reasonable possibility of being related to each of the study drugs, taking into account the disease, concomitant treatments, or pathologies, in order to individually adjust study drug doses.
- Treatment may be suspended for a maximum of 21 days to allow sufficient time for recovery. Cycle delays >21 days due to an AE require discontinuation of all study treatments.
- Any additional questions related to dose adjustments may be discussed with the Lilly CRP/CRS.
- For Parts A and B only.
 - if the AE is, in the opinion of the investigator, more likely due to 1 drug than another, adjustment drug causing the toxicity should be adjusted, and the dosing and schedule of the other study drugs may be maintained.
 - if the roles of each agent are impossible to separate, all involved therapies should have dose adjustments and/or suspensions.
 - refer to irinotecan and temozolomide prescribing information for additional dose modification guidelines.

See Section 6.6.1.3 dose modification tables for guidance specific to Part C.

